2. OBJECTIVES

Primary Objective:

In this randomized, double-blind, controlled study, we aim to investigate the effects of consumer expectancy, related to either gluten-containing or gluten-free oat bread on short-term (within 8 hours) overall GI symptoms in individuals with NCGS.

Hypothesis:

We hypothesize that expected gluten intake via bread consumption (as influenced by verbal information), but not the actual gluten intake increases subjective overall GI symptom score in individuals with NCGS. (see Figure 1, comparison E+G- vs. E-G-).

Expectation Intervention

[figure not shown]

Figure 1. Overview of group comparison related to the primary objective (*i.e.* comparing E-G- vs. E+G- groups). (E- = Expectancy of getting gluten-free bread, E+ = Expectancy of getting gluten-containing bread, G + = actual gluten-containing bread, G- = actual gluten-free bread).

Secondary Objective(s):

 To investigate the effects of the actual intake of gluten on overall symptoms in individuals with NCGS.

Hypothesis:

We hypothesize that expected bread consumption (E+ or E-) (as influenced by verbal information), but not the actual bread composition (G+ or G-) affects subjective GI and extra-intestinal symptoms in individuals with NCGS.

- To investigate the effects of expected gluten intake and actual gluten intake on individual GI and extra-intestinal symptoms in individuals with NCGS.

Hypothesis:

We hypothesise that in participants who expect to receive gluten-containing bread, there will be an increase in GI and extra-intestinal symptoms regardless of the actual bread composition (G+ or G-) in individuals with NCGS.

- To study the impact of emotional well-being on overall, intestinal and extra-intestinal symptoms after expected or actual gluten intake in individuals with NCGS.

Hypothesis:

We hypothesize that individuals with decreased emotional well-being (as measured by PHQ-9, PHQ-15 and GAD-7) are more vulnerable to expectation in relation to gluten intake (as influenced by verbal information) leading to more symptoms.

- To investigate the effects of expectation and/or actual intervention on mood (affective) changes in individuals with NCGS.

Hypothesis:

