4.4 Sample size calculation

Sample size calculation is based on our primary outcome measure, the overall symptom score, using a visual analogue scale (VAS). Since no data of overall symptom score based on expectancy in an NCGS population are available, we based our sample size calculations on a well-designed study most comparable to the present study by Biesiekierski et al. (2013) (17). In that study, the effects of gluten on GI symptoms in patients with NCGS after dietary reduction of fermentable, poorly absorbed, short chain carbohydrates (17) were examined. They reported an increase in mean overall symptom score after the ingestion of either 16g gluten/day (high-gluten arm) of 10.3mm in VAS-score with a standard deviation of 12.8mm (data obtained by requesting raw data from author (17)). In the study of Biesiekierski et al. (2013) a change of 20mm in VAS of overall symptom score was considered clinically relevant. Since our study has a different study design in which expectancy may play a major role and symptom scores may increase less, we deem an overall symptom difference in VAS-score of 15mm to be clinically relevant. Using a difference in overall mean symptoms of 15mm with a standard deviation of 12.8mm, power of 80% and two-sided alpha of 0.05, a sample size of 20 participants per group are required. So, a total sample size of 80 participants is required.

In addition, in order to account for potential drop outs due to drop-out after randomisation and during the test day for a reason other than intolerable symptoms, we ask permission to include max 5% (*i.e.* 4) extra participants, resulting in maximal 84 participants in total. Power analysis was conducted in the statistical power analysis program "G*power, version 3.1 for Macintosh" (19).

Version number: 3.0, date 16-12-2020

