7.2 Randomisation, blinding and treatment allocation

After screening and subsequent inclusion in the study, each participant will be assigned to a unique participant identifier code. Participants will be randomly assigned to one of the following experimental conditions:

- 1. Gluten-free expectation and actually receiving gluten-free oat bread (E-, G-).
- 2. Gluten-free expectation but actually receiving gluten-containing oat bread (E-, G+).
- 3. Gluten-containing expectation but actually receiving gluten-free oat bread (E+, G-).
- 4. Gluten-containing expectation and actually receiving gluten-containing oat bread (E+, G+).

The randomisation lists will be generated by an independent co-worker from the same department as the principal investigator who is not further involved in the study, using a publicly available procedure through the internet (http://randomizer.org). This random number generator performs balanced permutations, resulting in an equal number of participants per treatment order followed. Participants will be randomly allocated to the treatment conditions and there will be a stratification on gender using block randomisation (block sizes of 8). The randomisation scheme will be up to n=90, this to be sure in case of dropouts, to randomize potential (new) participants to a new randomization number.

The investigator has no access to the randomisation list that conceals the intervention code. However, since expectation may play a role in the experience of symptoms, the investigator is unblinded to the expectation arm since the investigator has to inform the participant about allocation to the gluten-free or gluten-containing expectation group. Of course, the investigator is blinded to the actual treatment. The randomisation list will be kept in a sealed envelope by the head of the department (prof. dr. [name]), to reveal the treatment in case of medical emergency. Primary investigators of all participating centres will receive the contact details of prof. dr. [name]. The condition numbers as allocated by the independent colleague, who will carry out the randomisation, are registered by the investigator in the screening and enrolment log. Furthermore, the same co-worker will keep the randomisation lists. The "randomization key" will be provided to the investigator only after all experimental and statistical procedures have been completed.

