9.1 Primary and secondary study parameter(s)

The main research question will be analysed by means of repeated measures univariate analyses of variance (ANOVA) with Expectancy ("gluten-containing" vs. "gluten-free") and Gluten ("gluten-containing bread" vs. "gluten-free bread") as between-subjects factors and Time (baseline and after intervention) as repeated measure factors on the several dependent measures including changes in overall (GI) symptom score, gastro- and extraintestinal symptoms, positive and negative affective parameters, and well-being. Only significant main- or interaction effects revealed by these procedures will be further examined by post-hoc univariate tests, corrected for multiple comparisons.

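### The primary comparison is E+G- vs E-G- in section 2, but section 9.1 names no primary effect and reaches that comparison only as a gated, corrected post-hoc

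*Protocol*

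**What the plan says.** **Objective and hypothesis (Protocol, section 2).** The primary objective concerns the effect of expectancy on "short-term (within 8 hours) overall GI symptoms in individuals with NCGS". The hypothesis points to one comparison, "see Figure 1, comparison E+G- vs. E-G"-, and the Figure 1 caption repeats those two groups as the comparison for the primary objective.

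**Sample size (Protocol, 4.4).** The calculation is for a difference between two groups: "Using a difference in overall mean symptoms of 15mm with a standard deviation of 12.8mm", with "power of 80% and two-sided alpha of 0.05, a sample size of 20 participants per group are required". It then multiplies by four: "So, a total sample size of 80 participants is required". It does not say which two groups the 15 mm separates, and it mentions neither an ANOVA nor a multiplicity correction.

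**Analysis (Protocol, 9.1).** The main research question goes to a repeated measures ANOVA with Expectancy and Gluten between subjects and Time (baseline, after intervention) within subjects. No term is named as the one that answers the question, and E+G- vs E-G- is not mentioned. Follow-up tests are conditional: "Only significant main- or interaction effects revealed by these procedures will be further examined by post-hoc univariate tests, corrected for multiple comparisons". Neither the correction method nor the number of comparisons is given.

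**The concern.** The hypothesis and the analysis specify different tests of the main question. E+G- vs E-G- isolates expectancy, because nobody in those two cells eats gluten. The pooled Expectancy effect averages that comparison with E+G+ vs E-G+, where belief and real gluten coincide in one arm. A positive pooled effect could therefore come wholly from the gluten-containing bread, and the trial's conclusion would depend on which result is taken as primary. The protocol does not say which.

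The comparison that section 2 does name is permitted only after another effect is significant, and then at a stricter level than the 0.05 used in section 4.4. How much that matters depends on how the gate is read.

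**Working it through.** **Inputs.** Difference 15 mm, SD 12.8 mm, two-sided alpha 0.05 and 20 per cell (section 4.4); equal allocation (section 7.2: "resulting in an equal number of participants per treatment order followed"). I take 12.8 mm as the SD of the change score, since section 4.4 attaches it to a reported increase. With two time points, the Expectancy x Time test equals the Expectancy test on change scores, so the checks use a 2x2 ANOVA on change.

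**1. The protocol's own figure.** n per group = 2 x (1.960 + 0.842)² x (12.8/15)² = 11.4, so 12 by normal approximation and 13 by the t-test. The stated inputs do not give 20. Twenty per group is more than they require. It is also the number needed at alpha 0.05/6, but section 4.4 states 0.05, so a built-in correction cannot be assumed.

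**2. The direct contrast.** Standard error = 12.8 x √(2/20) = 4.05 mm, and 15/4.05 = 3.71. Two-sample t power with 20 per group:

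| Level | Power at 15 mm |
|---|---|
| 0.05 | 95.1% |
| 0.05/2 | 91.0% |
| 0.05/3 | 87.9% |
| 0.05/4 | 85.4% |
| 0.05/6 (all pairwise tests, assumed) | 81.5% |

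**3. Can the pooled effect and the direct contrast disagree?** Suppose only E+G+ rises, by 15 mm, and E+G- equals E-G-. The pooled Expectancy difference is (0 + 15)/2 = 7.5 mm, with standard error 12.8 x √(1/40 + 1/40) = 2.86 mm and ratio 2.62. By simulation:

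- Expectancy is significant in about 74% of trials.
- E+G- vs E-G- at 0.05 is significant in 5%, its type I error.
- Expectancy is significant without a significant interaction in about 19%.
- Expectancy is significant with neither Gluten nor the interaction significant in about 5%.

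**4. What the gate costs.** Power of E+G- vs E-G- at 0.05/6, for a true 15 mm difference:

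| True pattern | Ungated | Gate opened by any significant effect | Gate opened only by the interaction |
|---|---|---|---|
| 15 mm in both breads | about 82% | about 82% | about 3% |
| 15 mm in gluten-free bread only | about 82% | about 82% | about 68% |

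The 3% arises because an equal effect in both breads means no interaction, so the gate opens only by chance (5%). That is the pattern the protocol predicts: section 2 expects symptoms to follow expectation regardless of the bread eaten. The interaction-only reading is also a natural one. Each factor has two levels, so a significant main effect leaves nothing further to separate, and within-bread comparisons conventionally follow an interaction. Yet section 9.1 refers to main or interaction effects, which also allows the wider reading.

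**The case against.** **Power.** A reader might infer that the gate and correction leave the primary comparison underpowered. The protocol's inputs do not support this. If any significant effect opens the gate, its cost is negligible, and even a six-test Bonferroni correction leaves about 81.5%. Six is itself an assumption. Power of 42% can be produced by combining that correction with a 10.3 mm effect, but section 4.4 gives 10.3 mm as an earlier study's result and sizes the trial on 15 mm. This objection stands, except under the interaction-only gate.

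**Misreading.** It can also be said that a pooled effect driven by E+G+ would not pass unnoticed. In that scenario Gluten or the interaction is usually significant too, follow-up tests would be run, and a false E+G- vs E-G- result at 0.05/6 is rare (under 1%). This softens the concern. But the interaction is silent in about 19% of trials, and a warning from another term does not tell the reader which result is the trial's primary answer.

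**The objective's wording.** The objective speaks of expectancy generally, which would fit a factorial Expectancy effect on 40 vs 40. That would be a coherent primary, but it is not the comparison in the hypothesis and Figure 1.

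**The sample size.** A reader might say section 4.4 was calculated for E+G- vs E-G-. That is a reasonable inference from its two-group form, but the section names no contrast.

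**Type I error.** With several ANOVA terms tested, a reader might also infer an inflated error rate. The chance that some term is significant is not an error rate for the primary comparison, and the gate and correction make that comparison conservative.

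**Conclusion.** The protocol contradicts itself on its primary test. Section 2 and Figure 1 define E+G- vs E-G-; section 9.1 assigns the main question to an ANOVA with no primary effect named and treats that comparison as a conditional, corrected follow-up. The difference is substantive: about 74% against 5% significant when the effect lies only in E+G+.

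A shortfall in power below 80% is not established on the stated inputs. It appears only under the interaction-only gate, and section 9.1 does not settle whether that gate applies. The figures assume normal change scores, a common SD of 12.8 mm, 20 completers per cell and, where a correction is shown, Bonferroni over the stated number of tests. The contradiction itself depends on none of these. It is not detail that can be left to a later analysis plan, because the protocol already fixes two incompatible answers.

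**What to change.** In section 9.1, name the change in overall GI symptom score for E+G- vs E-G-, estimated from the four-cell model, as the single primary test at two-sided 0.05. State that it is carried out whatever the ANOVA terms show and without multiplicity correction. Make Expectancy, Gluten and their interaction secondary, with estimates and 95% confidence intervals, and apply the correction only to the remaining pairwise tests. In section 4.4, name the contrast being sized and the inputs that give 20 per group.

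If the sponsor intends the pooled Expectancy effect as primary, change the hypothesis, Figure 1 and section 4.4 accordingly, and keep E+G- vs E-G- as a named secondary contrast.

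Either route is a wording amendment, to be made before unblinding. It needs no extra participants or data. With 20 per cell, the ungated contrast has about 95% power at 15 mm.

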9.2 Other study parameters

Baseline characteristics will be described as means and standard deviations (in case of normal distribution) or medians and interquartile ranges (in absence of a normal distribution) for continuous variables and frequencies for categorical variables.

10. ETHICAL CONSIDERATIONS

10.1 Regulation statement

This study has to be approved by the Medical Ethical Committee of Maastricht University (METC). The study will be conducted according to the Declaration of Helsinki (64th WMA General Assembly, Fortaleza, Brazil, October 2013), the Medical Research Involving Human Subjects Act (WMO) and the FDA guidelines for the conduct of clinical trials. The general principles of informed consent, ethics review and data management will be in line with Good Clinical Practice (GCP).

10.2 Recruitment and consent

After approval of the study by the METC of MUMC+, recruitment will take place via MUMC+, Amsterdam UMC and WUR. Participants will be recruited via the outpatient clinic of the gastroenterology department and of the dietetics department of the participating study sites. Eligible individuals with NCGS will be informed by their treating physician during their visit to the outpatient clinic or "stadspoli", or local GP practices. The treating physicians will give oral and written information to eligible individuals with NCGS and will inform them that a researcher will contact them once if they are interested in receiving further information regarding the study. Further information will be provided verbally or via email by the researcher and the written information brochure will be sent by regular mail or email. A time period of one week (minimum) is provided to decide whether the participant would like to participate. The participant is asked to contact the investigator by telephone or email if he or she would like to participate. If the participant does not contact the researcher however, the researcher will contact the participant once (at the earliest 7 days after sending the written information brochure, and only if the participant has given permission to do so during the first conversation). Thereafter, an appointment with the researcher will be made to sign an informed consent.

Lists available in the participating centres, with potential eligible subjects (e.g. IBS, NCGS/NCWS and controls) who have previously indicated that they can be contacted about future studies, will also receive one single mailing with containing the advertisement text with the study information. This mail will be sent by the local administrator of the database or local researcher of the participating centre. Furthermore, volunteers will be recruited by means of advertisements on the website of the "Prikkelbare Darmsyndroom Belangenvereniging", "Coeliakie vereniging", local and faculty newspapers, and social media, as well as by using posters in publicly accessible sites such as the hospital, university, health centres, pharmacies, gyms, bakeries and relevant shops (such as "the

Bisschopsmolen" in Maastricht (http://www.bisschopsmolen.nl) and e.g. restaurants serving gluten-free meals), and the website www.onderzoeksmachine.nl ("see also document "E3_Advertentietekst_NL64850.068.18_Versie2.0_02-10-2019"). Additionally, the recruitment website Proefpersonen.nl (https://www.proefpersonen.nl), which is facilitated by the company Link2Trials, will be used for recruiting and pre-screening eligible subjects. Volunteers enrolled in their database will be pre-screened by Link2Trials based on age. If they match these criteria, they will receive the advertisement text from Link2Trials. Furthermore, the advertisement text will be placed on their website, which is accessible to both volunteers already registered at Link2Trials and unregistered volunteers. Potentially interested volunteers will contact the coordinating researcher by e-mail or telephone, and will subsequently receive the written information brochure by e-mail or regular mail. Enrolment in the Link2Trials database is not necessary to obtain the researchers contact information, but is voluntary if subjects are interested in receiving information about other research.

If a volunteer is interested in participation in this study, he or she can contact the research team by e-mail or telephone, as given on the advertisement.

Participants can always contact the researcher or independent medical doctor if any question will arise and will be referred to the VWS brochure "General information for research participants" that contains general information about medical-scientific research. The researcher will contact the interested individuals by e-mail or telephone and send them the PIF via e-mail or general mail. Participation will be on voluntary basis. Before the start of the study, volunteers will be given written information about the study, its aim and the measurements. A time period of one week (minimum) is provided to decide whether the participant is willing to participate. The participant is asked to contact the investigator by telephone or email if he or she would like to participate. If the participant does not contact the researcher however, the researcher will contact the participant once (at the earliest 7 days after sending the written information brochure, and only if the participant has given permission to do so during the first conversation). Permission to contact the patient by telephone will be logged in the subject screening and enrolment log. Thereafter, an appointment with the researcher will be made to sign an informed consent. All participants will have to sign an informed consent prior to the screening in duplicate. The informed consent form has to be filled out completely. Both the participant and researcher have to sign the form at the same time. Date of assignment is necessary. The participant will directly receive a copy of the signed informed consent form.

Due to COVID-19, informed consent can also be obtained without an on-site appointment. After the researcher provided verbal information over the phone, participants will receive

the PIF plus attached informed consent form in duplicate via general mail. They will be asked to sign one copy and return this via regular mail. Upon receivement, the researcher will also sign the informed consent form. Only after obtaining the informed consent the screening will be performed via a (video)call.

Privacy of the participants will be protected, which means that the study results will be related to an identification code. Codes and related participant information will not be available to individuals others than the investigator and the project leader and will be stored in a password-protected file. Participants can, at any time, make an appeal to the independent doctor (Drs. [name] of MUMC+) that has been appointed to this study. Participants will be informed that their decision to participate is totally voluntary and they can withdraw at any time without giving a reason. Participants have the opportunity to be informed about the group results at the end of the study.

10.3 Objection by minors or incapacitated subjects (if applicable)Not applicable.

10.4 Benefits and risks assessment

Participants will not receive any direct benefits as a result of participating in this study. The screening visit does, however, include a general health check, which would provide beneficial information for the participant. An indirect benefit of this study will be the insights into the effects of expectation of consuming gluten on overall symptoms and thus the tolerability of gluten in non-coeliac gluten sensitivity. Moreover, this study will provide information on which bread type leads to symptoms in this specific population of people with non-coeliac gluten sensitivity. There are some small burdens participants can experience during this study. First, the time that they will invest at home by filling out guestionnaires (which takes about 5 minutes in total each day). Secondly, participants have to visit the MUMC+ on 2 occasions for: a 1-hour screening visit and one test day visit which takes almost the entire day (from 8.00AM - 4.30PM) for the bread (i.e. gluten-free or glutencontaining) intervention. Moreover, in a subgroup of participants a blood test (by venepuncture) will be taken to exclude coeliac disease by means of serological tests on anti-tTG IgA. This requires participants to make an additional 20-minute visit to the MUMC+ prior to the screening visit, may lead to minor discomfort and can cause small and transitory hematoma/bruises to appear.

Bread intervention

Participants will record in daily diaries any signs of illness, medication used, any deviations from the protocol and adverse events. The study breads are safe and commercially available. Bread itself is a harmless food product, which is widely consumed daily by the general population worldwide.

Gluten-containing oat bread

Participants may experience mild GI symptoms after the consumption of the study bread, since the included participants suffer from self-reported gluten sensitivity. It should be noted that the consumption of gluten by non-coeliac gluten sensitive participants does not lead to coeliac-specific antibodies and villous atrophy or any allergy related processes in participants with NCGS and exclusion of coeliac disease (21). The gluten-containing study bread contains an amount of gluten comparable to that is present in normal commercially available bread and consumption of 4 slices of this bread does not exceed the average amount of gluten that is normally consumed per day. Moreover, the risk of consuming gluten for 1 day is considered to be very low, especially considering the fact that coeliac patients are excluded.

Oat bread

The included participants follow a gluten-free/gluten-restricted diet because of the experience of symptoms induced by wheat- or gluten-containing food products. These gluten proteins do not occur in oats, which means that oats can be used to create safe food products for people with coeliac disease and non-coeliac gluten sensitivity (31).

